needle and then withdraw the needle leaving the tubing in the skin. Any hyperemia related to the insertion subsides in about 60 minutes. When the hyperemia induced by inserting the tubing in the skin subsides, the experiment begins. During this time Lactated Ringer's perfuses the tubing. The researchers tape a fiber optic laser Doppler flowmeter probe and its holder over each microdialysis site. The researchers control the temperature of the holders. The holders start at 33°C (91.4°F). During the experiment, the computerized data acquisition system records heart rate, skin blood flow, and skin temperatures continuously. The researcher and/or an automated critical care monitor measures blood pressure at 5-7 minute intervals.

Local Heating Protocol: The intradermal microdialysis probes are randomly numbered 1 or 2 and assigned to receive doses of Lactated Ringer's (probe 1) or Losartan (probe 2).

Probe 1. Lactated Ringer's only

Probe 2. Lactated Ringer's + Losartan

Initially, Lactated Ringer's flows through all probes. Then the investigational agents are added to the Lactated Ringer's flowing through MD probe 2 for 60 minutes. When the skin blood flow is stable, we perform a 20-minute baseline and set of measurements, including placement of 3 ECG electrodes for the collection of heart rate. After we have collected baseline data, we begin the dose-response protocol. We add identical concentrations of C21 to the perfusate in probes 1 and 2. At 10-minute intervals, we increase the concentration of C21 in the perfusates in identical fashion in probes 1 and 2. The participant receives 10 different concentrations of C21. After perfusing the last concentrations, all MD sites are then warmed to 43°C (108°F) to perform Maximal Skin Blood Flow. At the same time, the researchers switch the fluids at all sites to Ringer's + SNP for about 30 minutes. This causes the blood vessels at the MD sites to dilate or enlarge as much as they can. The researchers then de-instrument the subject, remove the microdialysis fibers, and apply sterile dressings. The subject is given verbal and written instructions for how to care for the microdialysis sites. The researcher measures final vitals before the subject departs.

VII.E.7 *Will you attempt to recontact subjects who are lost to follow-up?*
No - followup is not required in this study

VII.E.9 *Will subjects be provided any compensation for participating in this study?*
Yes

VII.E.10 *Cash*
No

VII.E.11 *Gift Card*
No

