No

XI. Data Analysis

XI.1

Describe the analysis methods you will use, including, if applicable, the variables you will analyze

The primary outcome variable will be cutaneous vascular conductance, which is calculated from laser-Doppler flux/mean arterial pressure. Three-way repeated measures ANOVA (group, MD site, dose) will be used to examine group differences and local microdialysis treatment differences across the doses of pharmacological stimuli. Appropriate post-hoc analyses with corrections for multiple comparisons will be performed when main effects are identified, including potential confounding variables as covariates. Paired t-tests will be used to examine group differences in subject characteristics.

XI.2

Provide the rationale or power analysis to support the number of subjects proposed to complete this study.

Using previously published data that determined differences in cutaneous vascular conductance (CVC), an index of skin blood vessel dilation, the results of a power analysis indicated that 24 young men and women (12 subjects x 2 groups) will be sufficient to detect a meaningful physiological difference (power=0.80, $\alpha=0.05$) of a ~10% change in CVC from baseline between microdialysis treatment sites and sex differences (men and women). Based on the available literature and on prior experience with microdialysis studies, the standard deviation of the difference is ~10%. After accounting for attrition, withdrawals, and screen failures, we conservatively estimate that 44 people will need to be consented and screened in order to arrive at this target number of 24.

XII. Future Research

XII.1

Do you wish to keep any information about subjects involved with this research project so that members of the current research team may contact them in the future for your own research projects?

Yes

XII.2

Do you wish to keep any information about subjects involved with this research project so that [other researchers](#) may contact them for future research?

No

XII.3

List the data or information you will keep:

Name

Race/ethnicity

Birthdate

Sex

Contact information (mailing address, e-mail address, phone number)

XII.4

Does this project involve storing any data, tissues or specimens for future research?

Yes – contribution for future use is optional

XII.5

Describe how you will keep track of those who consent to future use and those who do not and how you will prevent future use for those who do not consent.

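### Balance the losartan probe's forearm position within each sex and put it in the model: a cheap gain in precision, not a correction of bias

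*Combined protocol and SAP*

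**What the plan says.** Each participant has two microdialysis probes. Under Local Heating Protocol in VII.E.6, "The intradermal microdialysis probes are randomly numbered 1 or 2"; probe 1 carries Ringer's alone and probe 2 Ringer's plus losartan. The numbering therefore decides which place on the arm gets losartan. The method of randomisation is not stated, nor is any balancing within sex. The insertion text in VII.E.6 asks only that sites avoid veins. It names no standard positions and does not say that position is recorded.

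XI.1 plans a "Three-way repeated measures ANOVA (group, MD site, dose") on cutaneous vascular conductance (CVC). There, MD site stands for the local treatment, so physical position is not a named factor. Covariates are allowed, but none is named, and they are mentioned with the post-hoc analyses.

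XI.2 sets the size at "24 young men and women (12 subjects x 2 groups"), for a difference of about 10% and with the statement that "the standard deviation of the difference is ~10"%. I.5 states H2, the losartan effect, for both sexes.

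**The concern.** Position is to the two probes what period is to a two-period crossover: a nuisance factor that is crossed with treatment by randomisation and is usually balanced and fitted. If CVC, or the response to C21, differs systematically between the two places, each person's losartan-minus-control difference gains or loses that amount according to the layout drawn. Left out of the model, this scatter enlarges the error of the H2 contrast. With 12 people per sex, an uneven split can also move the estimate in the one sample the trial will have. What is at stake is precision, mainly for H2 read separately in women and in men.

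**Working it through.** **Inputs.** From XI.2: difference 10, SD of the difference 10, alpha 0.05 (taken as two-sided; the plan does not say), 12 per sex. Assumption: a position effect d, the difference between the two positions on the same scale, of 5 points, with a range of 3 to 7. The documents give no value.

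**The plan's own figure.** For a paired contrast, power comes from the noncentral t with noncentrality (10/10)·√n. Ten people give 0.803 and 12 give 0.883, so 12 per sex is ample for the site contrast. As a two-sample sex contrast with SD 10, the normal approximation gives 13 per group one-sided (power 0.789 at 12). The two-sided t-test at 12 per group has power of only 0.65. That is a separate and larger matter than position.

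**Chance of an uneven split, if randomisation is simple.** With X ~ Binomial(12, 0.5):
- 9:3 or worse in one sex: 0.146.
- In at least one sex: 1 − (1 − 0.146)² = 0.27.
- The sexes differ by 4 or more in the number with a given layout: 0.152.

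**Shift in the realised estimate.**
- H2 in one sex at 9:3: d·(9 − 3)/12 = 5 × 0.5 = 2.5 points (1.5 to 3.5 for d = 3 to 7).
- H1 at the control site, sexes differing by 4: 5 × 4/12 = 1.67 points.
- H1 as the group main effect over both sites: 0, because each person contributes both positions.

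**Validity.** In 40,000 simulated trials with simple randomisation and no position term, the mean H2 estimate under the null was 0.00 to 0.02, and type I error was 0.049 to 0.050 for d from 0 to 10.

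**H2 power for a 10-point effect, SD 10 excluding position.** Unmodelled, the SD is √(100 + d²); at d = 5 it is √125 = 11.18. Balanced and modelled, the SD is 10 with one degree of freedom fewer.

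| d | One sex (n = 12), unmodelled | One sex, modelled |
|---|---|---|
| 0 | 0.883 | 0.876 |
| 3 | 0.855 | 0.876 |
| 5 | 0.805 | 0.876 |
| 7 | 0.734 | 0.876 |

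In all 24 people, d = 5 gives 0.987 unmodelled and 0.997 modelled. If H2 needs significance in each sex, joint power at d = 5 is 0.805² = 0.65 against 0.876² = 0.77.

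**If the stated SD of 10 already contains position scatter.** At d = 5 the residual SD is √(100 − 25) = 8.66, and per-sex power rises from 0.883 to 0.949 (0.904 at d = 3, 0.992 at d = 7).

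**Balance without the model term.** In the simulation, type I error for H2 in all 24 fell to 0.028 at d = 5 and 0.005 at d = 10. The error term still carries position scatter that balance has removed from the estimate. The two changes belong together.

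**The case against.** The strongest reply is that randomisation has already dealt with position. That stands. A reader might infer that an uneven split biases the losartan contrast, but the estimate is unbiased over randomisations and its error term covers the chance imbalance. A reader might also infer that the sex comparison is compromised. H1 is exposed only if it is tested at the control site, which the plan does not say. Even there, type I error stays at about 0.05, and d = 5 lowers power only from 0.650 to 0.623.

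Four further points carry weight.
- Simple randomisation is itself an inference from the word randomly, and the split probabilities depend on it.
- XI.2 is framed as "10% change in CVC from baseline between microdialysis treatment sites and sex differences (men and women"), and VII.E.6 records a baseline before C21. A constant position difference cancels from change from baseline and from the site-by-dose interaction. To matter there, position would have to alter the response to C21.
- No common positions are defined in the text available; an attached microdialysis document may say more. If the layout varies freely between people, a fixed position term cannot remove the scatter.
- The gain in all 24 is about one percentage point, and at d = 5 the unmodelled per-sex power of 0.805 still meets the planned 0.80.

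The covariate allowance helps less, since it names no variable and does not commit the analysis to position.

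These points limit the claim and shape the remedy. They do not remove it, because H2 is stated for both sexes and the change costs little.

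**Conclusion.** The point holds as an inexpensive improvement in precision. As described, the plan randomises forearm position without balancing it within sex and leaves it out of the model, so any systematic position effect stays in the error of the losartan contrast. For an assumed 5-point effect and an SD of 10 that excludes it, the gain is 0.805 to 0.876 within one sex and about 0.987 to 0.997 overall. At 3 points the per-sex gain is about 2 percentage points (0.855 to 0.876).

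These sizes rest on an assumed position effect, on positions being consistent between people, and on an outcome from which the effect does not cancel. The documents do not support a finding of bias in H2 or inflated type I error, nor any effect of an additive position difference on H1 as a group main effect.

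**What to change.** In VII.E.6, define two standard forearm positions, for example proximal and distal, still avoiding veins. State the randomisation method: assign the losartan position from a permuted-block list (block size 2 or 4) kept separately for women and men, so that each sex ends near 6:6. Record the position used.

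In XI.1, add position as a fixed effect, with position-by-dose where the dose response is tested, since a main effect alone cannot act on the site-by-dose term. Say whether CVC or its change from baseline is analysed, and whether H1 is tested over both sites or at the control site.

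The cost is one allocation list, one recorded variable and one degree of freedom for the position main effect (per-sex power 0.883 to 0.876 if position is irrelevant). Position-by-dose over the ten concentrations takes a further 10 − 1 = 9 from the dose-level error. No extra probe, visit or participant is needed.

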Visit 2- Experimental Visit (approximately 4 hours)

Note: In the event of an experimental failure (e.g. equipment stops working, building power outage during study visit, etc) subjects may be asked to repeat a trial.

Experimental procedures

Regularly menstruating women and women taking hormonal contraceptives will be tested during the early follicular/placebo phase to minimize variability due to circulating sex-steroid hormones. Participants will be asked to fast 3 hours prior, avoid alcohol and forms of heavy exercise 24 hours prior, avoid caffeine 12 hours prior, and avoid supplements and over-the-counter medications the morning of the experimental visit. Participants should NOT stop taking medications as prescribed by their physician.

Subjects will come to the Pharmaceutical Sciences Research Building (PSRB) and be escorted by a member of the research team to 118 PSRB for the blood draw and experiment (intradermal microdialysis). A blood draw involves a research nurse or trained lab personnel drawing blood (15 ml, ~1 Tablespoon) for substances of interest (e.g. reactive oxygen species) and blood chemistry.

Microdialysis Probe Insertion: (NOTE: The intradermal microdialysis insertion procedure used here is identical to the one approved in IRB #201909818, #202006148, #202009357, #202203433, and #202104188) Please see the attached "intradermal microdialysis" document for general information about intradermal microdialysis, schematic representation of the procedure, and references. The researchers place a tight band around the forearm so they can visualize veins. For each MD site, they make pairs of pen-marks on the arm 2.5 cm (1 inch) apart and away from veins. They remove the tight band. The MD tubing enters and exits the skin at the marks. The researchers clean the arm with povidone iodine and alcohol, and place an ice bag on the site for 5 minutes to numb the skin. Then they insert a thin needle into the skin at each entry mark. The needle's tip travels between the layers of skin for 2.5 cm (1 inch) and exits the skin at the matching exit-mark. They thread the microdialysis tubing through the

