VII.E.12 *Check*
Yes

VII.E.13 *Who will be providing the research compensation check to the subject?*
Accounting Services directly via the e-Voucher system

VII.E.16 *Other*
Yes

VII.E.17 *Describe:*
Parking vouchers will be provided during study visits.

VII.E.18 *If you plan to compensate subjects using cash, checks or cash equivalent does your unit have a [Cash Handling Procedure](#) in place that has been approved by Accounting Services?*
Yes

VII.E.19 *Describe the compensation plan including*

- *Compensation amount and type per visit*
- *Total compensation*
- *Pro-rating for early withdrawal from study*

Experimental visits:
\$15/microdialysis probe
\$7.50/hour for completing the experiment

Total for completing the study: \$60 (one completed study visit)
Parking pass for time involved at study and screening visits.

Pro-rating: Subjects can receive payment for pre-treatment and experiments not completed. The researchers pay an amount of money equal to the part completed. For instance, if a subject completes half of Experiment 1, the subject receives \$15.00 for each probe inserted plus \$7.50 for each hour they completed. The researchers may ask subjects to repeat a trial. If subjects agree to repeat a trial, they receive payment for the repeated trial as stated above.

VIII. Risks

VIII.1 *What are the risks to subjects including*
- *emotional or psychological*
- *financial*
- *legal or social*
- *physical?*

Physical Risks:

Microdialysis: Intradermal microdialysis is a specialized research technique. [name] is highly skilled in this technique and has been using the procedures in this protocol (including fiber placement, perfusate preparation, subject monitoring, and fiber removal) for over 10 years with no

adverse events and have been reviewed and approved by [name] at the University of Iowa.

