- Electronic records (computer files, electronic databases, etc.) - Data will be entered using subject ID code into the ICTS REDCap web-based database application that is password protected. REDCap questionnaires will be filled out on the participants electronic device (e.g. phone, tablet, personal computer) or a printed paper copy if they prefer. No personal identifiable data will be entered. Only research staff on the IRB approved study will be allowed access this database. The ICTS REDCap staff are responsible for maintaining security of the data. Some data using subject ID code will also be entered into a Microsoft Excel and SPSS datasheets that will be kept in a shared server for CLAS that is password protected. Only research staff on the IRB approved study will have access to the folder the study on the server.
 - Name - [REDACTED]
 - Title - IT Support Consultant
 - University Job Classification - Faculty/Staff
- Biological samples (blood draws, cheek swabs, saliva samples, tissue samples, etc.) - Blood samples will be sent to the UIHC pathology lab for analyses. Remaining biological specimens, such as blood, will be labeled with subject code, date collected and IRB protocol number and transported to the PIs laboratory (118 PSRB) in a secure unbreakable biohazard container. Samples will be stored in the PIs laboratory in a -80C freezer in 111 PSRB. All samples will be labeled with date collected and subject ID code only. No personal identifiable information will be labeled on the sample. Only the PI and her research staff will have access to the samples.
 - Name - [name]
 - Title - Assistant Professor
 - University Job Classification - Faculty/Staff

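### The planned repeated measures ANOVA drops a participant who loses one probe; a properly specified mixed model would keep the usable site, for a modest gain

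*Combined protocol and SAP*

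**What the plan says.** Section XI.1 names one model for the primary outcome: "Three-way repeated measures ANOVA (group, MD site, dose) will be used to examine group differences". The outcome, CVC, is "calculated from laser-Doppler flux/mean arterial pressure", so each value needs both a flux and a blood pressure reading.

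Section VII.E.6 describes the experiment. One probe carries Ringer's alone and the other Ringer's plus losartan. "We add identical concentrations of C21 to the perfusate in probes 1 and 2", and the concentration rises every 10 minutes; "The participant receives 10 different concentrations of C21". Flux is recorded continuously, and the team or a monitor "measures blood pressure at 5-7 minute intervals".

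On incomplete experiments, VII.E.6 says that after an experimental failure "subjects may be asked to repeat a trial". VII.E.19 makes the repeat depend on the participant's agreement and sets payment for partial completion: "Pro-rating: Subjects can receive payment for pre-treatment and experiments not completed". Section XI.2 plans for 44 consented to reach 24, allowing for attrition, withdrawals and screen failures.

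No section gives a rule for missing cells, and neither a mixed model nor imputation is mentioned. The only software clue is in X.4: "Some data using subject ID code will also be entered into a Microsoft Excel and SPSS datasheets". That concerns data storage and does not name an analysis procedure.

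**The concern.** A conventional repeated measures ANOVA needs every within-person cell. If one probe fails, the participant leaves the whole three-way model, including the part that the other probe could still inform.

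Hypothesis 1 (section I.5) compares the C21 response of women and men. The Ringer's site answers that directly, so discarding it because the losartan probe failed wastes relevant data. It also wastes a four-hour visit and two needle insertions already undergone. With only 12 per sex planned, each lost participant counts. The loss falls mainly on the sex comparison, which has the least power to spare.

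**Working it through.** **Inputs.** From the documents: 12 per sex, power 0.80, alpha 0.05, difference about 10%, SD of the difference about 10% (XI.2); two probes and ten concentrations (VII.E.6). Assumed, because the documents do not give them: the missing rate, two-sided testing, and a between-person SD of 10% for the sex comparison.

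**1. The plan's own figure.** For the paired site comparison, n = (1.96 + 0.84)² × (10/10)² = 7.85, so 8 by the normal approximation and 10 by the t distribution. At n = 12 the t power is 0.883, so 12 is consistent with this comparison. For the two-sample sex comparison, n per group = 2 × 7.85 = 15.7, so 16 (17 by t). At 12 per group the two-sided t power is 0.649. A one-sided normal calculation gives 13 per group, close to 12. The stated size therefore leaves little or no slack for the sex comparison.

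**2. Cells per person.** 2 sites × 10 concentrations = 20, or 2 × 11 = 22 if baseline is a level.

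**3. Behaviour of the method.** A standard repeated measures ANOVA routine refused to fit once a single cell was removed. The usual alternative is listwise deletion.

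**4. Loss of whole probes.** If each probe fails independently with probability q, expected complete cases = 24 × (1 − q)², and expected participants losing both probes = 24 × q².

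| q | Complete cases (ANOVA) | Losing both probes |
|---|---|---|
| 5% | 24 × 0.9025 = 21.7 | 0.06 |
| 10% | 24 × 0.81 = 19.4 | 0.24 |

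A mixed model loses only those in the last column. The table assumes no repeat and no replacement.

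**5. What the lost participants cost.** Two-sided t power for the sex comparison (difference 10, SD 10) is 0.65, 0.61, 0.56 and 0.51 at 12, 11, 10 and 9 per group. The complete cases above are about 10.8 and 9.7 per group.

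**6. What a mixed model recovers.** Simulated power for the sex effect, complete-case analysis against mixed model:
- Between-person SD 8, within-person SD 7, 400 runs: 0.69 against 0.72 at 5% probe loss; 0.60 against 0.66 at 10%.
- Participant-mean SD near 10, 150 runs, Monte Carlo error about 4 points: 0.65 against 0.65 with nothing missing; 0.65 against 0.67 at 5% probe loss.

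The gain is therefore 2 to 6 points, and at 5% it is not clearly distinguishable from simulation error. The two sets use different variances, so compare figures only within a set, and not with step 5.

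**7. Which mixed model.** Null simulations on complete data (12 per group, 2 sites, 10 doses; 4,000 runs at participant SD 8, site SD 4, residual SD 5) tested group-by-dose with random effects for participant and site within participant only. The false-positive rate was about 0.07 to 0.27, depending on how widely dose slopes were assumed to vary between people. With no slope variation but AR(1) correlation of 0.7 it was about 0.10. A Greenhouse-Geisser-corrected ANOVA gave 0.03 to 0.05 throughout. An uncorrected ANOVA gave 0.10 and 0.15 in the two settings where the simple mixed model gave 0.16 and 0.27. A dose-related participant effect or covariance is therefore needed.

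**The case against.** A reader might infer much heavier losses. If single cells vanished independently at 0.5%, 1% or 2%, the share of participants with a gap, 1 − (1 − p)²⁰, would be 9.5%, 18.2% or 33.2% (10.4%, 19.8% or 35.9% with 22 cells). The documents do not support that mechanism. Flux is continuous over each 10-minute step, and with blood pressure every 5 to 7 minutes a step has one or two readings. The failures that VII.E.6 names, equipment stopping and a power cut, lose a probe or a visit. Where the whole visit is lost, no model recovers it.

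A reader might also infer bias from early stopping related to response or discomfort. That is speculative: VIII.1 says pain is unusual once the probe is in place, and a mixed model would not repair dropout driven by something unrecorded.

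Nor is the payment clause evidence that incomplete visits are expected. It answers a standard form prompt about early withdrawal. Repeats are allowed, and 24 is the number meant to remain from 44, so the table in the working may overstate the shortfall. These points stand and limit the size.

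Two further points are fair. The ANOVA procedure is unnamed, some programs fit a mixed model under that label, and VII.B.11 refers to a separate protocol. Post-hoc comparisons are also unspecified, and those at a single site need not drop anyone. Neither supplies a rule for missing cells in the main model. The repeat is optional and tied to experimental failure, and the 44-to-24 allowance names only person-level losses.

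**Conclusion.** The point holds at modest size. As conventionally fitted, the XI.1 model drops a participant from the whole analysis after one probe failure, although the other site remains usable. At an assumed 5% or 10% independent failure rate per probe, without repeat or replacement, 24 becomes about 21.7 or 19.4 complete cases. Keeping the partial data is worth about 2 to 6 points of power for the sex comparison under the assumed variances. With complete data the simulation showed no power difference. Losses of a fifth or a third of participants would require scattered, independent cell loss, and the documents give no reason to expect it. The change is worth making because it is cheap, provided the replacement model carries the dose-related correlation.

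**What to change.** In XI.1, replace the three-way ANOVA with a linear mixed model fitted to all available site-by-dose data:
- fixed effects: group, site, dose and all their interactions;
- random effects: participant, and site within participant;
- a participant-level dose effect: either a random dose slope or a stated within-site covariance across doses, such as AR(1);
- Kenward-Roger or Satterthwaite degrees of freedom.

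Name the software procedure, and check that it offers the chosen covariance and degrees-of-freedom method.

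The cost is wording and one decision: the covariance structure must be fixed before the data are examined. No new data, visits or procedures are needed. The model still assumes data are missing at random, so the report should list how many probes and steps were lost, by sex and site, and why.

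### XI.1 sets no baseline reference for CVC and ties post-hoc tests to main effects, so a difference already present before C21 can be read as a C21 response

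*Combined protocol and SAP*

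**What the plan says.** Section XI.1 defines the endpoint: "The primary outcome variable will be cutaneous vascular conductance, which is calculated from laser-Doppler flux/mean arterial pressure". The model follows: "Three-way repeated measures ANOVA (group, MD site, dose) will be used to examine group differences and local microdialysis treatment differences across the doses". Then: "Appropriate post-hoc analyses with corrections for multiple comparisons will be performed when main effects are identified, including potential confounding variables as covariates". XI.1 mentions no baseline subtraction and no scaling to baseline or to maximum. It does not say whether the baseline period counts as a dose level, and it does not name the model term that answers either hypothesis.

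Section XI.2 sizes the trial for an approximate "10% change in CVC from baseline between microdialysis treatment sites and sex differences (men and women"), and adds that "the standard deviation of the difference is ~10" percent.

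The hypotheses in I.5 concern dilation in response to C21: larger in women than in men (H1), and larger with losartan than without it in both sexes (H2).

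The order of events is in VII.E.6. After a Ringer's period at both probes: "Then the investigational agents are added to the Lactated Ringer's flowing through MD probe 2 for 60 minutes". Next: "When the skin blood flow is stable, we perform a 20-minute baseline and set of measurements". Ten rising C21 concentrations then go to both probes. At the end: "After perfusing the last concentrations, all MD sites are then warmed to 43°C (108°F) to perform Maximal Skin Blood Flow", with a switch to sodium nitroprusside (SNP). Baseline and maximum are thus both recorded, but no section says how either enters the analysis.

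**The concern.** A main effect of site or sex on CVC level averages over dose. It adds whatever difference existed before C21 to whatever difference C21 produced. H1 and H2 are about the second part only.

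The exposure is clearest for H2. By the time baseline is recorded, probe 2 has had 60 minutes of losartan and probe 1 has had none. If blocking AT1 receptors changes resting tone, that change is carried through all ten C21 concentrations and appears as a site main effect, even if C21 acts identically at both sites. For H1, a resting sex difference in CVC would do the same to the group main effect.

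Main effects are the only trigger that XI.1 states for further testing, and XI.2 uses a scale that XI.1 does not adopt. The readings that the text allows (level, percent of maximum, absolute change, percent of baseline) can give different answers from the same data, and nothing fixes the choice before the data are seen.

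**Working it through.** **1. The plan's own figure.** XI.2 gives difference 10, SD 10 (standardised difference 1), power 0.80, alpha 0.05, 12 per sex; sidedness is not stated. A paired two-sided t-test needs 10 subjects and has power 0.883 at 12. A two-sided comparison of the sexes needs 17 per group by t (16 by normal approximation) and has power 0.649 at 12 by t. A one-sided normal calculation gives 13 per group and power 0.789 at 12. So 12 fits a site contrast within one sex, and fits the sex contrast only approximately and one-sided. The present point does not depend on this.

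**2. Algebra.** Write CVC at site *s* and dose *d* as a(s) + r(s,d), where a is the resting level and r the C21 response.
- Site main effect on level = [a(losartan) − a(Ringer's)] + [mean r(losartan) − mean r(Ringer's)].
- Change from own-site baseline contains only the r terms.
- With baseline kept as a dose level, site × dose also drops a constant a.

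The same holds for sex.

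**3. Assumptions for the illustration.** From the documents: 12 per sex, 2 sites, 10 concentrations plus baseline (11 levels). Assumed: variance 100 per observation, split 50 subject, 25 site, 25 residual; AR(1) residual with correlation 0.5; identical C21 response everywhere; two-sided 5%.

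**4. Additive losartan offset, test on level.**
- Variance of the residual mean over 11 levels: (25/11) × [1 + 2Σ(1 − k/11)0.5^k] = (25/11) × 2.64 = 5.99.
- SD of the within-person site difference: √[2 × (25 + 5.99)] = 7.87. Standard error with 24 people: 7.87/√24 = 1.61.
- Offsets 2.5, 5, 10 give noncentrality 1.56, 3.11, 6.22 on 22 df: significant in 32%, 84%, 100%.
- Absolute change from own-site baseline: about 5% in simulation at every offset.
- Site × dose with baseline included, Greenhouse-Geisser corrected: 3–4%.

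**5. Additive sex offset, test on level.** Per-person SD: √(50 + 30.99/2) = 8.09. Standard error: 8.09 × √(2/12) = 3.30. Noncentrality 0.76, 1.51, 3.03: significant in 11%, 30%, 82%. Absolute change at the Ringer's site: about 5%.

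**6. Sensitivity.** Across the other variance splits, correlations and simple t-test versions tried:

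| Offset | Site main effect | Group main effect |
|---|---|---|
| 2.5 | 20–35% | 9–15% |
| 5 | 54–95% | 22–43% |
| 10 | 99–100% | 65–94% |

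**7. Do the other provisions remove the offset?**
- Adding each person's mean baseline CVC as covariate: site main effect still 31%, 84%, 100%. One value per person cannot adjust a difference between two sites in that person.
- Level as percent of maximum (assumed mean maximum 150, between-person SD 20, site SD 10): 20%, 62%, 99%. Change in points of maximum: 4–5%.

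**8. Does one baseline-referenced scale always work?** No.
- *Additive offset, percent of baseline* (assumed resting CVC 50 or 100, top response 20 or 50): significant in 5–8%, 6–21%, 10–56%, on average in the direction of a smaller response with losartan.
- *Proportional difference* (losartan site 10% or 20% higher throughout; resting CVC 50, linear rise to a top response of 50): the mean rise is 27.5, so absolute change differs by 2.75 or 5.5. The simulated SD of change is 5.15 per site, so the site difference in change has SD 5.15 × √2 = 7.28 and standard error 7.28/√24 = 1.49. Noncentrality is 1.85 or 3.70: significant in about 42% or 94%. Percent of baseline stays near 5%. The level main effect is worst: mean level 75, differences 7.5 or 15, significant in 99% or 100%.
- Factor × dose terms in CVC units share the weakness of absolute change, because a proportional gap widens as CVC rises.

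**The case against.** **The model already contains the right terms.** A three-way ANOVA yields sex × dose and site × dose, and XI.1 speaks of differences across doses. The main-effect clause governs post-hoc tests; it does not say that main effects decide the hypotheses. This stands in part. A reader might infer that XI.1 commits the trial to raw CVC level and will report a false effect. The text does not support that: it leaves scale and deciding term open. But nothing makes the interactions decisive, so the misreading remains available.

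**XI.2 supplies the scale.** It sits directly below XI.1 and speaks of change from baseline. That is a fair pointer to intent, but XI.2 describes planning, not analysis, and its percentage could mean points or percent of baseline.

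**The covariate clause or normalisation to maximum covers it.** Baseline CVC is not named as a covariate and normalisation is not stated. As the check shows, neither a person-level covariate nor a level in percent of maximum removes a between-site offset.

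**Absolute change is no safer than percent of baseline.** This stands. A reader might infer that percent of baseline should be ruled out because an additive offset does not cancel on it. The documents do not say whether a resting difference would be additive or proportional, and under a proportional difference the ranking reverses.

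**The offsets are invented, and a separate protocol exists.** Both are true. No section reports a resting difference by site or sex, so the percentages illustrate and do not predict. VII.B.11 records a separate written protocol, not available here, which may already settle the scale.

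**Conclusion.** The concern holds for the text supplied. XI.1 does not separate the C21 response from a difference present before C21, although both hypotheses and the sample size refer to response or change. On level, an additive site offset of half the assumed SD produces a significant site main effect in about 84% of trials with no difference in C21 response (54–95% across the settings tried). The corresponding figure for sex is about 30% (22–43%). Change from own-site baseline stays near 5%.

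These figures rest on assumed offsets and variances. The simulated SD of change is about 5.1, not the roughly 10% in XI.2, so they show false support only and say nothing about power. The gap in the text does not depend on them.

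Replacing main effects on level with a baseline-referenced contrast was an improvement under both the additive and the proportional differences examined. Which baseline-referenced scale is best cannot be settled from the documents. This should be fixed before analysis; it does not call the design or the data collection into question.

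**What to change.** In XI.1:
- Judge H1 and H2 on a baseline-referenced response, not on main effects of CVC level. Either use change in CVC from each site's own 20-minute baseline, or keep baseline as a dose level and use group × dose for H1 and site × dose for H2, with a sphericity correction.
- Tie post-hoc tests to the chosen terms instead of to main effects, and list the covariates.
- State the scale in advance: CVC units, percent of the 43°C plus SNP maximum, or percent of baseline. If percent of maximum is used, it still needs the baseline reference.
- Name either absolute change or percent of baseline as primary and report the other as a sensitivity analysis, since the first cancels an additive resting difference and the second a proportional one.
- Report resting CVC by site and sex.

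In XI.2, use the same scale and say whether the 10% means points or percent.

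The summary over concentrations, the site used for H1, and whether H2 must hold in each sex separately are the sponsor's choices, but they should be written down because they affect power. If XI.2's difference of 10 and SD of 10 apply to the chosen contrast, two-sided power is 88% per sex for H2, 78% for both sexes (0.883²) and 65% for H1. If the 10% applies only at the top concentration and the difference grows linearly, the mean difference over ten concentrations is 5.5. With SD still 10, the powers are then about 41%, 17% and 25%, although averaging may lower the SD.

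The cost is a few sentences; baseline and maximum are already recorded. The drawbacks are that baseline noise enters a change score and that no single scale is neutral to every form of resting difference. If the separate protocol already fixes the scale and terms, copying them into XI.1 is enough.
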